E. Protection of Human Subjects

1. Risk to subjects:

a. Sample

The proposed study will include 60 persons with dementia (PWD) and 60 caregivers (CGs) from 5 respite care centers (RCCs), approximately 33-57 ADC volunteers or staff and administrators/managers (will participate but are not considered subjects). The total number of persons counted for the Enrollment Tables is 180 persons. Both the PWD and his/her CG will be enrolled in this study and the PWD must attend one of the RCC sites for care at least once weekly. Additionally, volunteers will be enrolled who are long-time (defined as volunteering for at least 3 months or longer), and are present at least weekly. RCC Staff will have current affiliation with or have worked at the RCC with the last 12 months and are amenable to commit to the 6 month length of the study.

This is a cluster-randomized trial so each RCC whether in the EUC or PaM groups will be added every 2 months. For both types of conditions, the involvement of these participants includes: recruitment, consent and enrollment into the study; gathering of baseline data including an analysis of the percent of food eaten pre- and post-meals via a still photo, other assessments collected by an in-depth interview that will take about 1 hour. At this point in the **Intervention (PaM) group**, a train-the-trainer program will now be shared with RCC staff in the intervention site and within two weeks, under the direction of the Program Manager and with input from the

Registered Dietician, the RCC volunteer or RCC Staff will work with the CG to devise an initial plan of care for the PWD; this plan will be operationalized both at home and in the RCC (see Intervention – Partners at Meals). Additional training for new volunteer and booster sessions are planned. Monthly the RCC volunteer or RCC Staff and CG ‘partnership’ (dyad) will meet to determine if the plan is still working, and if adjustments need to be made with the help of the Program Manager or his/her designated staff member, and Registered Dietician, if needed. The intervention lasts 6 months and during that time, data are collected every month. Reasons for withdrawal are: death, institutionalization, and discharge from the RCC. Additionally, the administrator/manager of the RCC will be interviewed every 3 months that the project is ongoing (could be up to 2.5 years) to determine their satisfaction with the project, use of resources, and willingness to sustain the project.

Those in the **Enhanced Usual Care (EUC) group** will have data collected at the same intervals (baseline, monthly or withdrawal) and the administrator/manager will be interviewed every 3 months. At the conclusion of the project in each site for those in the EUC sites, the Program Manager will provide the initial training sessions to the RCC volunteers at these sites.

The persons with dementia (PWD) and the caregivers (CG) could be considered vulnerable groups. Enrollment including the informed consent process and their continued participation will be based on several issues. All conversations, assessments and consenting will occur in a private room in the RCCs. The PI is very familiar with all of these sites and they all have a private room. The voluntariness of this research will be stressed every month that a CG completes their assessment; if a CG does not complete the forms requested every month after a second request, they will be asked by the Program Manager (not the RCC staff) if they consider the study to be in any way a burden, and will be withdrawn unless they state they wish to continue. PWD will be asked to assent to the Informed Consent and will be asked their assent to continue in the study every month. If at two separate times they decline, the PWD will be withdrawn from the study.

All CGs enrolled in the study, whether in the PaM or EUC arm, will receive \$50 at enrollment and **\$50 per month for every month** they are enrolled in the trial. It is expected that since the CGs live with or on the same property as the PWD, that this money will be considered shared. RCC volunteers or RCC Staff receive **\$100 for every CG with whom they partner**. Volunteers or RCC Staff receive \$100 for each PWD/CG dyad they work with for at least one month; there is no further remuneration. It is possible that over the life of the project within any agency, the volunteer may work with more than one PWD/CG dyad and thus be eligible for \$100 for each dyad with whom they assist. The total remuneration will be based on the total number; for example, if a volunteer works with 3 PWD/CG dyads, they would receive \$300. **The total number of dyads that any one volunteer or RCC Staff can work with is 5 and thus the maximum reimbursement would be \$500.** (This is below the \$600 limit for IRS reporting.) For every year that the site has participants enrolled in the study, they will receive **\$10,000 to provide for the extra resources, time, and data collection** that this study will impose.

To be eligible for the study, **potential PWDs will need to be:** aged 45+ years; receives 4 or more hours daily of care; Functional Assessment Staging (FAST) score of ≥ 4 with supervision required at mealtimes; not enrolled in hospice; not receiving enteral feeding or active treatment by a speech pathologist; not diagnosed with dysphagia. **Caregivers will need to be:** someone

who lives with or near the PWD who is also enrolled in this study; providing 4 hours of care/day; assisting with ADLs including meals. **RCC volunteers must be long-term volunteers (at least 3 months)** and must be present at the RCC at least weekly. RCC Staff that participate in the study will have current affiliation with or have worked at the RCC with the last 12 months and are amenable to commit to the 6 month length of the study.

Administrators/managers will be the Administrator/manager of record.

b. Sources of materials:

Research materials will be obtained directly from participant in-person or telephone interviews, direct observation with checklists, and direct standing weight obtained at the RCC. Data collected directly from participants that will be recorded include social, psychological, medical, functional, and health factors related to nutritional intake, weight, and dietary intake. All information obtained will be used solely for research purposes and participant confidentiality will be assured. This will be explicitly disclosed in the Informed Consent Form and carefully reviewed with potential participants. Private information, including name, address, telephone number, and address that are individually identifiable will be collected from study participants for the purposes of this research. Such private information will be coded and each individual will be assigned a study identification number. A key will be created to decipher the code. Only the PI and Co-I, Program Manager, Research Assistant, and Registered Dietitian will have access to this code. This is because they will be contacting caregivers in their homes. Furthermore, all data will be stored in the MUSC secure REDCap database, which was used successfully in our SCTR-funded pilot study.

c. Potential risks and planned protection:

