Family-managed care is critical in promoting quality of life (QOL) and health in Alzheimer's disease and other dementias. The Partners at Meals (PaM) intervention emphasizes focusing on more than just "changing" a PWD, but also intervening with the People with whom they interact and Place where meals occur. With this intervention, CGs and volunteers or staff at RCCs partner and modify mealtime at a point when the PWD is still able to express preferences and engage in the meal process, and develop a PWD-centered plan of mealtime care. Of note, our pilot work indicated that CG's report of mealtime behavior may be inaccurate because CG and other family members may overlook key cues/triggers to dysfunctional behavior. Thus, to **improve this identification process, a secure and HIPAA-compliant telehealth component (Doxyme)** is used to record dysfunctional behaviors displayed by the PWD on a 'tablet'. The CG interacts with their "partner" volunteer, the RCC staff or MUSC Interventionst (AIM 4) either through a real-time connection or sharing of the recorded file so that together, they can problem-solve issues and modify the plan of care. This CG-volunteer/ staff member partnership also fosters consistency across settings (AIMS 1-3), as well as imparts skills and self-efficacy for care management for both parties, improves QOL for the CG and the PWD, improves mealtime outcomes for the PWD, and promotes better health outcomes.

Research design. A randomized cluster-design trial will be conducted in two large RCCs with six sites that serve primarily white and African American PWDs. RCCs will be randomized to the **intervention condition (Partners at Meals; 2 sites)** or [**'enhanced usual care' (EUC)**] (4 sites). The primary unit of analysis is the PWD and CG: 60 PWDs, 60 CGs will be enrolled; it is estimated that up to 60 volunteers/staff/managers may be enrolled. The CG and RCC volunteer or staff member is another dyad for analysis, as is the RCC volunteer/staff member and the PWD. Additionally, RCC Managers at both PaM and EUC sites will be interviewed regarding barriers to implementation, ways to enhance the project, and possible causes of discharge of PWD from the study related to nutritional problems.

Additionally, to explore the feasibility of program replication and widespread adoption, an online

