Collaborating with the 2 respite care organizations and up to 180 subjects, a cluster design will be used to determine the efficacy of the Partners at Meals (PaM) train-the-trainer program compared to enhanced usual care (EUC). Two groupings of sites will be created in attempt to balance size and racial distribution: the largest site, which is racially diverse (The ARK), will be paired with a site (in the Respite Care Charleston system), which is not diverse: Together they will be one Site for treatment condition and analysis. The other four sites in the Respite Care Charleston system that together have approximately the same diversity and size, will be joined to create a second Site. These two Sites will then be randomized to PaM and EUC. All subjects (PWD, CG and RCC volunteers) will be followed for 6 months or until discharge or voluntary termination. The biostatistician will determine the cluster randomization. An ongoing process, impact and outcome monitoring plan is planned.

We will conduct an ‘enhanced usual condition’ training to identify ways that CGs communicate with family and friends to delegate challenging aspects of caregiving. Inspired by a unit of the Savvy Caregiver, the EUC will include a 30-minute presentation at sites with a follow-up 30-minute role-play regarding identifying challenging issues, ways of communication and ways to share those elements of caregiving that could be accomplished by others. When the site ‘comes on board’, the Program Manager will deliver the training and repeated every 6

months while the project is in progress for new CGs. Additionally, the staff of the EUC sites will be included in the teaching, and will facilitate discussion with the CGs during the interim. The program staff will attend the EUC site's support group every two months (or more frequently if needed) to see if CGs need guidance and discuss issues with the EUC staff.

Further, every attempt will be made to include PWDs with similar levels of cognitive/behavioral disabilities in both the PaM and EUC conditions; however, since this is cluster design, we cannot assure an equal balance.

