Exploratory AIM 4 includes MUSC research project staff to implement the intervention to CG and PWDS residing at home and receiving respite services. The past 14 months brought limitations to in-person meeting and programming in respite care centers affecting clients, volunteers and staff alike. Electronic platforms including Telehealth are now more commonly used and will be used to eliminate some of those barriers by making the intervention available to those not ready or able to engage in respite center programming or attending respite centers currently experiencing fewer Volunteers prior to the COVID pandemic.

Recruitment, enrollment, participant eligibility South Carolina is largely a rural state with more than 1/3 of the population identifying themselves as African American (AA). We recruit in through partnerships with agencies that serve a diverse group of families often in Medically Underserved Areas of South Carolina. Councils on Aging, homehealths, community centers and formal and informal respite centers are all places where Project Staff has formed connections to support and recruit for this project through web-based newsletters, through take-home fliers, social media announcements and announcing the study at support groups.

AIMS 1, 2 and 3 Eligibility criteria for the Volunteers or Staff; be a regular volunteer or staff with current affiliation of working or have worked at RCC within the last 12 months and is amenable to commit to the 6 month length of the study; able to read and speak English, identify as comfortable in the teacher/coach role, and demonstrate ability to use televideo and photograph.

(All AIMS) Eligibility criteria for Persons with Dementia (PWD): aged ≥ 45 years; diagnosis of Alzheimer's disease or related dementia with mild to moderate stage as demonstrated by the Functional Assessment Staging Scale (FAST) of 4 or greater; absence of wasting disorders (e.g., HIV/AIDS, heart or renal failure or COPD, end-stage cancer) ; some supervision required or dysfunctional behavior present (e.g., redirection); not receiving enteral feeding or active treatment by a speech pathologist/therapist; not diagnosed with dysphagia as identified by CG or on RCC Intake Sheet. Those enrolled in or qualifying for hospice will not be included.

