- Body weight and caloric intake – weight before meal in street clothing less outer garments; intake measured by images taken with tablet pre- and post-meals at pre-arranged times
- Edinburgh Feeding in Dementia Scale (EdFED XL with added questions) – 24-item scale for dysfunctional meal-related behaviors (images from the tablet may assist in validating behaviors in question)
- Quality of Life in Alzheimer’s Disease (QOL-AD) – 13 item instrument used in person with MMSE as low as 4

2. Caregiver measures:

Demographics collected only at baseline

- Age, race/ethnicity, employment, relation to PWD, living arrangement, hours/day caring for PWD

Outcomes collected baseline, monthly and completion

- Center for Epidemiological Studies – Depression Scale (CES-D) – widely used in CG studies
- Zarit 12-item Burden Scale – rated 0 – 4, used in prior CG studies
- European Quality of Life (Euro-QL) – measures health-related quality of life
- Self-efficacy for Change – based on CP3 Model (developed in pilot work)

3. Volunteer or RCC Staff measures (AIMS 1,2 and 3):

Demographics collected only at baseline

- Age, race/ethnicity, preparation for volunteer role including coursework or classes or personal experience as CG, frequency of attendance, years in role

Outcomes

- Self-efficacy for Change – based on CP3 Model instrument (developed in pilot work)
- Performance measures – self-report of fidelity to treatment, carry out or change mealtime plan, address questions, training issues, progress and participation (developed in pilot work)

4. RCC Administrator/Managers measures

Demographics collected only at baseline

- Age, education, training, years in role, roles and responsibilities, role as CG

Outcomes

- Overall satisfaction of staff and CGs
- Satisfaction with implementation issues, satisfaction with program, willingness to continue
- Discharge status of any PWDs in study – to institutional care, hospitalized related to nutrition-related problems

Online Global Survey of RCC providers

An online global survey of RCC providers will be conducted using a researcher developed survey instrument. The survey will explore RCC telehealth/video conferencing capabilities, their use pre and post the onset of the COVID-19 pandemic, and RCC provider attitudes and opinions towards communicating and delivering individualized and in-the home educational support services to caregivers and their families with these types of technologies.

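### The eligibility rule for mild-to-moderate dementia sets a minimum FAST score and no maximum, so it does not implement the stage the plan says it targets

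*Combined protocol and SAP*

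**What the plan says.** The criterion for persons with dementia (PWD) appears twice in the combined protocol and SAP.

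- **Section D, eligibility criteria for PWD (all Aims):** the diagnosis must be "with mild to moderate stage as demonstrated by the Functional Assessment Staging Scale (FAST) of 4 or greater". The same paragraph excludes enteral feeding, active speech-therapy treatment, diagnosed dysphagia and wasting disorders, and adds: "Those enrolled in or qualifying for hospice will not be included".
- **Section E.1.a, Sample:** the restatement asks for a "Functional Assessment Staging (FAST) score of ≥ 4 with supervision required at mealtimes". It carries no stage label, and its hospice clause is only "not enrolled in hospice".

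Other parts of the plan rely on an intended stage. Section A has caregivers and centre partners "modify mealtime at a point when the PWD is still able to express preferences and engage in the meal process". The Data and Safety Monitoring Plan (Section A, individual roles) calls the chance of dysphagia slight, and does so for people with mild-to-moderate disease.

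Section D lists FAST and the MMSE as baseline-only measures, and no MMSE limit appears in the eligibility text. QOL-AD is described as a "13 item instrument used in person with MMSE as low as 4".

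The Study Overview in Section C says "every attempt will be made to include PWDs with similar levels of cognitive/behavioral disabilities in both the PaM and EUC conditions", then concedes that a cluster design cannot guarantee balance.

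**The concern.** A screener who applies the number cannot exclude anyone for being too advanced. A screener who applies the label has to invent a cut-off. Two centres could apply the same text differently, and both would comply with part of it.

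Three things are at stake. First, the enrolled population may not be the one for which the rationale was written, namely people who can still state preferences and take part in the meal. Second, if those beyond that stage respond less, the average effect on weight and mealtime behaviour, the two outcomes the study is said to be powered on, would be smaller than in the target group. Third, Section C randomises two composite Sites, one to each arm. A wider severity range leaves more room for the arms to differ at baseline on a factor plausibly related to both outcomes.

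**Working it through.** **Step 1. Does anything else supply the missing upper limit?**

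| Criterion | Where | What it does |
|---|---|---|
| FAST | D and E.1.a | Minimum of 4 in both; no maximum in either |
| MMSE | D, measures | Recorded at baseline; no entry limit |
| Hospice | D and E.1.a | D excludes those enrolled or qualifying; E.1.a names enrolment only |
| Enteral feeding, active speech therapy, diagnosed dysphagia | D and E.1.a | Limit feeding and swallowing problems, not stage |
| Weekly attendance at a centre | E.1.a | Indirect filter; Aim 4 is meant to reach people not ready or able to take part in centre programming |

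Several rows remove part of the severe end. None of them marks where moderate stops.

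**Step 2. What could this cost?** The plan states no effect size, SD, alpha, power or intraclass correlation, and no stage mix or effect by stage. There is therefore no figure of the plan's own to reproduce, and what follows is an illustration on assumed inputs.

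Inputs:
- 30 PWD per arm (half of the 60 in Section A; the split by arm is not stated).
- Two-sided alpha 0.05, 80% power, individual randomisation, normal approximation (all assumed).
- *f*: share enrolled beyond the intended stage (assumed 10%, 20%, 30%).
- *r*: effect in that share relative to the target stage (assumed 0, 0.5, 1).

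Smallest detectable standardised effect: (1.960 + 0.842) × √(2/30) = 0.72.

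Diluted effect: d_eff = d × [1 − f(1 − r)].

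Inflation of the required n: 1 / [1 − f(1 − r)]².

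| f | r = 0 | r = 0.5 | r = 1 |
|---|---|---|---|
| 10% | 1/0.90² = 1.23 | 1/0.95² = 1.11 | 1.00 |
| 20% | 1/0.80² = 1.56 | 1/0.90² = 1.23 | 1.00 |
| 30% | 1/0.70² = 2.04 | 1/0.85² = 1.38 | 1.00 |

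If the true effect in the target stage is 0.72, the power with 30 per arm becomes:

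| f | r = 0 | r = 0.5 | r = 1 |
|---|---|---|---|
| 10% | 71% (d_eff 0.65) | 76% (0.69) | 80% |
| 20% | 61% (0.58) | 71% (0.65) | 80% |
| 30% | 50% (0.51) | 66% (0.61) | 80% |

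The inflation factors depend only on *f* and *r*. The power figures also depend on the assumed 30 per arm. They are optimistic, because clustering is ignored although there is one composite Site per arm.

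**The case against.** The strongest reply is that this is a wording slip in a plan that limits severity by other means. Section D states the stage in words, and the feeding, swallowing, hospice and attendance criteria work against very advanced disease. Monthly assent and a standing weight taken at the centre push the same way. Section E.1.a is a shortened restatement (it also omits the wasting-disorder exclusion), so its narrower hospice clause need not repeal Section D. All of this stands, and it defeats one tempting reading: that every severe stage is admitted. That is true of the FAST clause taken alone, not of eligibility as a whole.

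The reply also reaches the effect size. A reader might infer that the open-ended rule does dilute the effect. The documents do not support that. They give no stage mix and no effect by stage. Section A describes when meals are to be modified and does not set an entry limit. The intervention also works on the caregiver and the setting, and the plan of care is tailored to each PWD. People with more mealtime difficulty could have more room to improve on EdFED.

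Finally, severity can differ between two Sites within any FAST range, and Section C already says that balance is not assured. A maximum score would narrow the range but would not cure the imbalance. The QOL-AD remark is peripheral, since QOL-AD is not one of the outcomes the study is powered on.

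What the reply does not remove is the contradiction between label and rule, on which both the rationale and the dysphagia reasoning depend.

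**Conclusion.** The point holds as an inconsistency in the eligibility rule. A minimum FAST score is offered as proof of a stage that has an upper end. Neither statement of the criterion supplies that end, and no MMSE limit does so instead. PWD beyond the intended stage who are not caught by the other exclusions could enrol.

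The consequence is possible, not established. Across the assumed range the required sample grows by a factor between 1.00 and 2.04, depending entirely on the share beyond the stage and how that share responds, and neither is in the documents. The figures show what could be at stake and do not estimate a loss in this trial. Any added imbalance between the two composite Sites is likewise a risk whose size cannot be derived.

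The correction is worth making because it is specific, cheap and uses data already planned.

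**What to change.** 1. **Reconcile the stage label and the FAST rule in Sections D and E.1.a.** Either add an upper FAST limit, chosen by the investigators as the end of their moderate stage, or delete the mild-to-moderate label and restate the target population. If later stages are intended, the passages in Section A and the monitoring plan that assume an earlier stage should be brought into line.
2. **Reconcile the hospice wording** so that both sections exclude the same people.
3. **Prespecify baseline FAST and MMSE as covariates** in the weight and EdFED analyses, and report both by arm. The analysis text in the document covers the provider survey and sets out no model for these two outcomes, so the covariates have to be written into that model when it is specified.
4. **State the limit of the adjustment:** with one composite Site per arm, covariates cannot separate Site from treatment.

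Cost: a short amendment and no new data collection. A maximum would slightly shrink the recruitment pool. Two covariates use a little information with 60 PWD (two parameters if each is entered linearly). If enrolment has begun, which the document does not make clear, a new maximum changes eligibility part-way. The date of the change would then need to be recorded, and participants enrolled before and after it described.
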